### I. Background and Significance

Donor heart availability continues to be a limiting factor in the number of cardiac transplants performed in the United States. While heart failure prevalence continues to rapidly rise the number of annual transplants has remained unchanged over the last decade. This drives a growing disparity between cardiac organ supply and demand. In 2015 there were 4,183 patients awaiting cardiac transplant, while a total of 2,804 heart transplants took place. As there continues to be a definite shortage of transplant viable organs in the U.S., it is of paramount importance and in accordance with the OPTN Final Rule that available resources are handled efficiently; namely, that all potentially transplantable organs are recognized for their enormous value as scarce resources and utilized to their maximum potential for the maximum benefit (the principle of Utility).

In 2015 there were a total of 2,804 cardiac transplants performed in the United States. In Region 1, which encompasses the New England states, there were 262 patients awaiting a heart transplant and a total of 97 cardiac transplants performed. During the same one-year-period there were 41 HCV-positive donors who met standard criteria for cardiac donation, however these hearts were unfortunately discarded and not used for transplant given HCV-positivity.

It has been well established that there exists a quality of life and survival benefit for patients with end stage heart disease who receive a well-functioning cardiac transplant. Success with transplantation requires ongoing immunosuppression to prevent immune graft rejection, which can become complicated if persistent viral infection in donors is transmitted to recipients in the process of organ transplantation. However, given the severe shortage of available organs and significant waitlist mortality, the use of organs from HCV-positive donors has previously been considered. Unfortunately there are limited studies investigating cardiac transplant outcomes in recipients with either pre-existing or de novo HCV infection, but conclusions drawn from the existing data state that the presence of HCV infection post-transplant, and the subsequent need for interferon based therapy, has been associated with poorer post-transplant outcomes and an increased risk of graft rejection. These dated findings have led to guidelines recommending that otherwise acceptable heart donors be excluded on the basis of HCV infection.

It is important to note that the above risks associated with transplantation of HCV-positive donor hearts were all determined prior to the current era of HCV treatment. Heretofore, the options for HCV treatment in the setting of cardiac transplantation have been severely constrained. Traditional anti-HCV therapy has depended on Interferon as the linchpin of single or combination therapy, and these Interferon based regimens have been generally poorly tolerated and correlated with an increased risk of serious systemic side-effects. The potential association between the use of Interferon therapy and allograft rejection, necessitating a further increase in net immunosuppression to treat rejection, can cause an increase in viral replication, setting off a vicious cycle. This concern over graft rejection has been one of the most

formidable arguments against Interferon use in the immediate post-transplant setting. In addition to the Interferon-based HCV regimens being poorly tolerated and prone to complications, they have also produced underwhelming cure rates of approximately 50% (genotype 1).

Direct acting antiviral agents (DAAs) have dramatically improved treatment options and outcomes for patients with HCV in both the pre-and post-transplant setting. Modern DAAs offer exceedingly high cure rates with minimal side-effects as compared to previous Interferon based treatment regimens.

SOLAR-1 was a large, multicenter, randomized controlled trial of sofosbuvir/ledipasvir with weight-based ribavirin in 223 liver-transplant recipients infected with HCV genotypes 1 and 4, with a wide range of liver disease severity. The cure rate for 12 weeks of combination therapy was 96%. In patients with HCV without cirrhosis in the allograft, cure rates of many DAA regimens have been reported in the range of 95% or higher. The discontinuation rate for these medications is low and side effects rare. Importantly, the sofosbuvir-based regimens do not have major interactions with the commonly used post-transplant immunosuppressive regimens.

The daily, fixed-dose, of co-formulated sofosbuvir (400 mg)/velapatasvir (100 mg) (EpclusaTM) is similarly effective to its predecessor sofosbuvir/ledipasvir but has pan-genotypic activity. It is currently recommended as a first-line therapy for treatment-naïve, noncirrhotic HCV infection for genotypes 1-5. Reported cure rates in the non-transplant setting have been high in the 98-100% range. In the ASTRAL-1, ASTRAL-2 and ASTRAL-3 studies, more than 1,000 patients have been treated with EpclusaTM with an overall cure rate of 98%. EpclusaTM has not been approved in the U.S. for use in the post-transplant setting, but is approved in Europe based on existing safety and efficacy data. There is an ongoing study in New Zealand that has administered EpclusaTM for 4 weeks (starting immediately post-transplant). There have been no safety concerns and all recipients achieved rapid virologic suppression and remain negative through 4 weeks after completion of therapy. A second pan-genotypic DAA –glecaprevir (300mg)/pibrentasvir (120mg) (G/P, MavyretTM), has also recently been approved by the FDA. Reported cure rates are comparable to EpclusaTM (in the 99% range in ENDURANCE-1) and adverse reactions low with <1% of patients discontinuing therapy in the ENDURANCE-2 and ENDURANCE-3 trials. In light of these recent advances in HCV therapy, we believe that DAAs have the potential to play an important role in curtailing the current discard rates for HCV-positive donor organs. While the studies mentioned above are specific to liver transplantation, it is postulated that HCV cure, as confirmed by documentation of sustained virologic response (SVR), should be at least similar if not higher in transplantation of other non-HCV reservoir organs, such as heart. We hypothesize that utilizing DAA therapy can prevent or eliminate HCV infection post transplant when an HCV-positive heart is transplanted into a HCV naïve host.

If this approach proves successful, it has the potential to result not only in a large increase *in the number* of organs available in the cardiac donor pool but also an overall increase *in the quality* of organ offers. The reason for this is that, unfortunately, many potential donors who are HCV-positive belong to a young demographic, aged 18 to 35 years, who are now caught up in the national epidemic of opioid and intravenous drug abuse, their deaths resulting from drug overdosing. Sadly, despite availability of curative HCV therapies, very few intravenous drug users (IVDUs) are able to access these therapies. Thus, it is estimated that the HCV epidemic will continue to spread amongst young IVDUs throughout the foreseeable future. HCV-positive donor hearts originating from this potential donor cohort, by virtue of their young age and statistical estimates of projected allograft performance after transplantation, may be

some of the most robust in the cardiac donor pool. Demonstration of successful preemptive and/or immediate post-transplant treatment of HCV in this model could expand the viable cardiac donor pool and result in a reduction in morbidity, mortality, and long-term healthcare costs for patients with end stage heart disease.

***Please note, throughout this protocol the use of HCV-positive refers to HCV nucleic acid testing (NAT)-positive organs. We address evaluation and management of NAT-negative organs under the Study Procedures section of this document and in the separate Protocol Summary document.***

## **II. Specific Aims**

### ***Primary Objective - Aim 1***

Determine if preemptive administration of pan-genotypic direct-acting antiviral (DAA) therapy in cardiac transplantation prevents the transmission of hepatitis C virus (HCV) infection from an HCV-positive donor heart to an HCV-negative recipient patient..

### ***Secondary Objectives - Aim 2-3***

#### ***Aim 2***

Evaluate the safety and tolerability of pan-genotypic DAA therapy in patients undergoing cardiac transplantation.

#### ***Aim 3***

Determine the proportion of subjects with undetectable serum HCV RNA at study day 7, 14, 28, 56, 84, 112, 140, 224, and 365 in cardiac transplant recipients receiving pan-genotypic DAA therapy following transplant from an HCV infected donor

### ***Clinical hypotheses***

#### ***Hypothesis 1.***

We hypothesize that preemptive administration of pan-genotypic DAA therapy following cardiac transplantation will be well-tolerated and halt the development of HCV infection in a transplant recipient as evidenced by a negative HCV viral RNA at 12 weeks post treatment.

#### ***Hypothesis 2.***

We hypothesize that preemptive administration of pan-genotypic DAA therapy after HCV-positive donor heart transplantation will produce non-inferior survival results in recipient patients as compared to historical Scientific Registry of Transplant Recipients (SRTR) and The International Society for Heart and Lung Transplantation (ISHLT) data.

## **III. Subject Selection**

### **Cohort study (N=100)**

This is a single center study evaluating if preemptive administration of pan-genotypic DAA therapy in cardiac transplantation prevents the transmission of hepatitis C virus infection from an HCV-positive donor heart to an HCV-negative recipient. Up to 100 patients will be enrolled study wide, with up to 50 total patients receiving transplant and treatment with study drug. We plan to enroll all 100 subjects and perform all 50 transplants at MGH.

Patients will be selected based on their diminished likelihood of receiving a heart from the waitlist within a period during which they would be likely to succumb to severe comorbidities. This will be determined in part through use of a patient's listing status (1A, 1B, 2) and clinical judgment.

To ensure maximal benefit for the recipient, only high quality donor hearts will be accepted as determined by 'traditional' cardiac donor selection criteria. These 'traditional' donor criteria, based on expert opinion and transplant experience, include: age less than 55 years, no history of chest trauma or cardiac disease, no prolonged hypotension or hypoxemia, appropriate hemodynamics (mean arterial pressure >60mmHg, central venous pressure 8-12mmHg), ionotropic support less than 10mg/kg/min (dopamine or dobutamine), normal electrocardiogram, normal echocardiogram, normal cardiac angiograph (if indicated by donor age and history), and negative serologies other than hepatitis C (including hepatitis B surface antigen, and human immunodeficiency virus). Donors will be deemed acceptable if they meet 8 out of 8 traditional cardiac donor selection criteria.

## 1. Donor Inclusion/Exclusion Criteria

### *1a. Donor Inclusion Criteria:*

Brain death diagnosed

Detectable HCV RNA

Traditional Donor Selection Criteria Met - acceptable for transplantation per usual evaluation

### *1b. Donor Exclusion Criteria:*

Cardiac anatomical damage or significant pathology noted during recovery

Liver disease or signs of liver decompensation (splenomegaly, ascites, advanced fibrosis or cirrhosis)

Donor has been known to have previously received HCV treatment (interferon, ribavirin or DAA)

Any standard contra-indication to donation noted in donor (significant malignancy, infection with human immunodeficiency virus (HIV), prion-related disease, unusual infection).

## 2. Recipient Inclusion/Exclusion Criteria

### *2a. Recipient Inclusion Criteria:*

Recipient is Age  $\geq$  18 years

Met MGH transplant center criteria, listed for cardiac transplant

Able to sign informed consent

### *2b. Recipient Exclusion Criteria:*

Pregnant or nursing (lactating) women

HIV positivity

Any contra-indication to cardiac transplantation per center protocol

For study patients in whom EpclusaTM therapy is being considered, exclusion criteria includes patients on the following p-glycoprotein inducers or moderate to potent CYP inducers that cannot stop therapy: carbamazepine, phenytoin, phenobarbital, oxcarbazepine, rifabutin, rifampin, rifapentine, St. John's wort.

For study patients in whom MavyretTM therapy is being considered, exclusion criteria includes patients on the following medications who cannot stop therapy: carbamazepine, rifampin, St. John's wort, and ethinyl estradiol-containing oral contraceptives.

For any patient receiving pan-genotypic DAA therapy, the corresponding drug administration instructions will be followed as listed in the EpclusaTM or MavyretTM package insert. This includes review of potentially significant drug interactions and discontinuation or alteration in dosages and monitoring as

recommended. The Tables that will be followed can be found on the Epclusa™ package insert pg. 7 Table 2 and the Mavyret™ package insert pg. 8 Table 5.

A subset of patients awaiting cardiac transplant also require kidney transplant. The efficacy of DAAs in the treatment of donor derived HCV infection in kidney transplant has been documented in recent reports at the University of Pennsylvania and John's Hopkins Hospitals. Given this recent data, patients requiring simultaneous heart-kidney transplant (SHKT) are being considered for enrollment in this study. If patients screened for enrollment meet inclusion criteria for cardiac transplant, they will not be excluded based on the need for SHKT. Their case will be discussed with the study's transplant nephrologist, and enrolled accordingly with plans to update UNET listing status for SHKT HCV-positive transplant. As far as DAA therapy is concerned, if a patient is already undergoing treatment based on receipt of an HCV-positive heart, there are no changes in Epclusa™ or Mavyret™ therapy duration that would be required if a kidney transplant is also performed. In patients receiving SHKT, a patient's renal function and potential for delayed graft function (DGF) will come into play when determining initial DAA selection; we anticipate that Mavyret will be the therapy of choice in patients undergoing SHKT. As described above previously, we will adhere to the recommended dosing, medications adjustments, and monitoring as outlined in the Epclusa™ and Mavyret™ package inserts as documented in the detailed protocol.

Please note: Amiodarone use will not be a recipient exclusion criteria. This has been discussed with the cardiac surgeons and transplant cardiologists. For any patients on amiodarone prior to transplantation, pacing wires will be in place post-OHT (per usual protocol) with plans to monitor for bradycardia. In general patients no longer require amiodarone post-transplant, however to remain cautious during the wash-out period, the ability to pace symptomatically bradycardic patients will remain in place until amiodarone is out of the system or DAA treatment has been completed.

Standard of care at Partners includes confirming that female patients are not pregnant at the time of organ transplantation. For women of childbearing potential, a urine pregnancy test will be performed prior to enrollment. A negative result will be required at the time of transplant and prior to continuing study treatment.

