## V. Study Procedures

Prior to enrollment in the study, research staff will be working with patient insurance to confirm that the patient insurer will be covering the cost of HCV treatment. In the event that insurance does not agree to cover the cost of HCV DAA therapy, the cost of medication will be covered by pre-established hospital funds.

Patients will initially sign informed consent to be “waitlisted” for HCV-positive donor hearts under this protocol. At the time a heart transplant becomes available, the “waitlisted” patients will be contacted and again sign informed consent for transplantation (standard of care).

Upon receiving notification that an HCV-antibody (Ab) positive donor organ is available, we will review if the organ is nucleic acid testing (NAT) positive or negative. A pre-emptive treatment approach will be used in patients receiving NAT-positive donor organs, and a reactive treatment approach will be performed in patients receiving NAT-negative donor organs, as outlined below:

**A study patient who receives an HCV NAT-negative donor heart (or heart and kidney)** will be followed with HCV viral load (VL) testing per study protocol (on study days 1, 3, 7, 14, 28, 56, 84, 112, 140, 224, 280, and 365)

- If the study patient does not develop a positive VL during this 365 day duration they will not undergo treatment with DAA therapy.
- If the study patient does demonstrate seroconversion *with a positive HCV VL* then we will initiate pan-genotypic therapy per study protocol. A patient’s case will be reviewed and DAA selection made based on individual patient factors with plans to complete a DAA course and monitor for SVR at 12 weeks post-therapy completion.

Upon receiving notification that an HCV-positive donor organ is available with plans for transplantation, a patient’s case will be reviewed and the appropriate DAA selected based on individual patient factors including current labs, medications, and anticipated future post-transplant therapies for any interactions that would preclude safe administration of DAA. **A study patient who receives an HCV NAT-positive donor heart (or heart and kidney)** will be scheduled to receive preemptive treatment with one of the following pan-genotypic DAAs:

- co-formulated sofosbuvir (400 mg)/velapatasvir (100 mg) (EpclusaTM) given orally for a duration of 8 weeks post-transplantation.

OR

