## **VI. Biostatistical Analysis**

### Variables/Time Points of Interest

The primary variable of interest will be HCV RNA at the multiple time-points assessed during and after treatment.

The primary efficacy outcome “Prevention of HCV Transmission” will be determined by a negative HCV RNA test.

The safety outcomes include summation of treatment related adverse events and transplant rejection or patient mortality. On treatment eGFR, proteinuria, hemoglobin, and liver function tests will be summarized to assess safety.

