### Statistical Methods

Patient characteristics for this cohort (N=50 receiving HCV+ organ) will be presented with summary statistics for baseline demographics and clinical variables. The SVR12 rate will be presented and 95% CI constructed with the exact test. Mean and standard deviation for on-treatment laboratory values will be presented to analyze safety.

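### Heart-kidney recipients are eligible without a cap, but on-treatment eGFR is summarised with no split by organ received, so a few such patients would blur the renal safety summary

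*Combined protocol and SAP*

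**What the plan says.** The recipient criteria in Section III (2b) open the study to heart-kidney candidates: "If patients screened for enrollment meet inclusion criteria for cardiac transplant, they will not be excluded based on the need for SHKT". The only limit on their number is the overall ceiling of 50 treated patients. The same text says that a heart-kidney patient's "renal function and potential for delayed graft function (DGF) will come into play when determining initial DAA selection", and adds that "we anticipate that Mavyret will be the therapy of choice in patients undergoing SHKT". Section V puts recipients of a NAT-positive heart, or of a NAT-positive heart and kidney, on one treatment path.

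Aim 2 is a safety objective: "Evaluate the safety and tolerability of pan-genotypic DAA therapy in patients undergoing cardiac transplantation". Section VI (Variables/Time Points of Interest) states: "On treatment eGFR, proteinuria, hemoglobin, and liver function tests will be summarized to assess safety". Section VI (Statistical Methods) describes a single cohort, "Patient characteristics for this cohort (N=50 receiving HCV+ organ) will be presented with summary statistics for baseline demographics and clinical variables", and gives the laboratory method in one sentence: "Mean and standard deviation for on-treatment laboratory values will be presented to analyze safety". Neither part of Section VI mentions a display by organ received or by drug, or a change from baseline.

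**The concern.** Eligibility was widened to patients who receive a new kidney, and the analysis text was not adapted. Section III treats kidney graft function as important enough to influence drug choice, yet it plays no part in the safety summary.

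Under Section V, study drug starts within 7 days of transplantation and runs for 8 weeks. The on-treatment window therefore covers the new kidney's early function. In an SHKT recipient, eGFR in that window mainly tracks the graft: low if function is delayed, then rising. In a heart-only recipient it reflects native kidneys after surgery and under immunosuppression. A single mean and SD over both groups describes neither.

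The distortion can run in either direction, so a reader of the report could not correct for it without knowing how many SHKT patients there were and how their grafts behaved. At stake is the clarity of one named laboratory measure under a secondary aim.

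**Working it through.** The plan gives no eGFR mean, SD, change or SHKT count, and 50 is a ceiling rather than a calculated sample size. There is therefore no stated figure to reproduce. From the documents come N = 50 treated and eGFR as a safety measure summarised by mean and SD. Every eGFR value below is an assumption chosen to show scale.

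**Levels, early in treatment.** Assume heart-only mean 60 (SD 18) and SHKT mean 15 (SD 8), which supposes poor early graft function in the SHKT patients. With SHKT share p:

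- mean = (1 − p) × 60 + p × 15 = 60 − 45p
- variance = (1 − p) × 18² + p × 8² + p(1 − p) × 45²

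| SHKT of 50 | p | Mean | Shift | Variance | SD | SD relative to 18 |
|---|---|---|---|---|---|---|
| 1 | 0.02 | 59.1 | −0.9 | 317.52 + 1.28 + 39.69 = 358.49 | 18.9 | +5% |
| 3 | 0.06 | 57.3 | −2.7 | 304.56 + 3.84 + 114.21 = 422.61 | 20.6 | +14% |
| 5 | 0.10 | 55.5 | −4.5 | 291.60 + 6.40 + 182.25 = 480.25 | 21.9 | +22% |
| 10 | 0.20 | 51.0 | −9.0 | 259.20 + 12.80 + 324.00 = 596.00 | 24.4 | +36% |

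**Change, as grafts recover.** Assume a heart-only change of −5 and an SHKT change of +20 to +40. The combined change is (1 − p) × (−5) + p × (SHKT change).

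- 1 of 50: 0.98 × (−5) + 0.02 × 20 = −4.5, or with +40, −4.1.
- 5 of 50: 0.90 × (−5) + 0.10 × 20 = −2.5, or with +40, −0.5.
- The fall of 5 disappears entirely when p = 5/(20 + 5) = 0.20 (10 of 50), or with +40, when p = 5/(40 + 5) = 0.11 (about 6 of 50).

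Under these assumptions the effect is small with one SHKT patient and becomes material from about three to five. Its direction depends on whether delayed function or recovery dominates at the visit summarised.

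**The case against.** The strongest reply is that the plan is silent here and does not prescribe a wrong analysis. Section VI never says that transplant types will be combined. The N=50 wording sits in the sentence on patient characteristics, not in the one on laboratory values. A split could be added at reporting without touching conduct. This stands in part: combining the groups is inferred from one described cohort and the absence of any stratum. It is still what a programmer following the text would produce.

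The size rests wholly on assumed values. Section III speaks only of a subset of patients and of the potential for delayed graft function, so there may be no SHKT patients, or one, and the effect may be negligible. That stands.

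Individual renal problems would not be judged from a cohort mean. A transplant nephrologist discusses each SHKT case (Section III), adverse events are assessed at treatment visits, and safety is reviewed every three months (Section IX). The study calls itself a pilot and attaches no test or stopping rule to eGFR. These points limit severity but leave the summary no easier to interpret.

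Two stronger readings are tempting. A reader might infer that a comparison of the two antivirals would be confounded by organ type, since SHKT patients are expected to receive Mavyret. No such comparison is planned, so this is only a caution for later use of the data. A reader might also infer that separating SHKT patients would reveal the antiviral's renal effect. It would not: there is no control group, and heart-only eGFR also reflects the transplant and immunosuppression.

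**Conclusion.** The point holds as a minor, reporting-level improvement. SHKT recipients may enter without a cap, and the eGFR summary does not separate them. On the assumed levels, the mean moves by 0.9 to 9 units and the SD grows by about 5% to 36% as the SHKT count goes from 1 to 10 of 50. With none there is no effect. Recovery of the new kidneys would move the summary in the opposite direction.

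The documents do not support saying that the renal safety result will be wrong, or that a true decline will be hidden. Complete masking of a fall of 5 needed about 6 to 10 SHKT patients under assumed gains of 20 to 40, and nothing in the documents indicates such numbers. The SVR12 analysis is unaffected.

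**What to change.** In Section VI, Statistical Methods:

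- State the number of SHKT recipients treated.
- Present on-treatment eGFR by visit, and its change from day 0, for heart-only recipients as the main renal summary.
- List SHKT recipients individually, with eGFR by visit, delayed graft function status and the antiviral received.
- Say that the heart-only summary is descriptive and does not estimate an antiviral effect.
- Treat proteinuria the same way only if it is measured. Section VI names it, but the visit schedule in Section V lists no urine protein test, and the two should be reconciled.

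SVR12 can stay as planned. The cost is a few table rows and a short listing. Organ received and drug given are necessarily known for every patient; delayed graft function status would need to be captured if it is not already. The one downside is slightly fewer patients in the main renal summary. With an assumed SD of 15 for change, the standard error goes from 15/√50 = 2.12 to 15/√40 = 2.37 if as many as 10 are SHKT. Eligibility, treatment and sample size do not change.
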